NCT04556838
Clinical Study VVN001-CS201
Protocol
17 June 2020

VIVAVISION BIOTECH, INC.
Clinical Protocol VVN001-CS-201
FINAL

Protocol Number: VVN001-CS-201
Protocol Title: A Phase 2a, Double-Masked, Randomized, Vehicle-controlled Trial Evaluating the Safety and Efficacy Activity of 1% and 5% VVN001 compared to Vehicle in Subjects with Dry Eye Disease
Sponsor: VivaVision Biotech, Inc.

Medical Monitor:

Issue Date: Original: 17June2020

Approved:

<<Other Signatories>>

Date

VIVAVISION BIOTECH, INC.
Clinical Protocol VVN001-CS-201
Investigator Signature Page

Protocol Number: VVN001-CS-201

Protocol Title: A Phase 2a, Double-Masked, Randomized, Vehicle-controlled Trial Evaluating the Safety and Efficacy Activity of 1% and 5% VVN001 compared to Vehicle in Subjects with Dry Eye Disease

Sponsor: VivaVision Biotech, Inc.

Issue Date: Original: 17June2020

Contact for Serious Adverse Events:

Investigator Name (printed or typed):

Investigator's Signature:

Date

SYNOPSIS

Protocol Number: VVN001-CS-201	Investigational Product: VVN001 Ophthalmic Solution
Protocol Title: A Phase 2a, Double-Masked, Randomized, Vehicle-controlled Trial Evaluating the Safety and Efficacy Activity of 1% and 5% VVN001 compared to Vehicle in Subjects with Dry Eye Disease	
The objectives of the study are: 
• Evaluate the safety and tolerability of VVN001, 1% ophthalmic solution and VVN001, 5% ophthalmic solution when administered BID compared to vehicle administered BID.• Evaluate the efficacy activity of VVN001, 1% ophthalmic solution and VVN001, 5% ophthalmic solution administered BID compared to vehicle administered BID in the treatment of signs and symptoms of Dry Eye Disease (DED).	
Study Population: The study population will consist of subjects with documented diagnosis of Dry Eye Disease.	
Number of Subjects/Study Sites: Approximately 165 subjects will be randomized to VVN001 or vehicle at approximately 10 centers in the United States (U.S.).	
Study Products: VVN001 ophthalmic solution or vehicle ophthalmic solution will be supplied as Investigational Product (IP).	
Route and Duration of Administration: IP will be instilled bilaterally in each eye BID (morning/evening) for up to 84 days.	
Study Design: This is a Phase 2a, multi-center, double-masked, randomized, vehicle-controlled, parallel-group study designed to evaluate the safety and tolerability and to explore the efficacy activity of VVN001 ophthalmic solution versus vehicle in subjects with dry eye disease. The study will consist of two periods over a 14-weeks total as follows: 
• Screening/Run-In period (Day -14 to Day -1)• Treatment period (Day 1 to Day 84) Screening/Run-In Period. At Visit 1 Screening (Day 1 minus 14 days), subjects who meet inclusion/exclusion criteria will begin a two-week run-in period during which they will be treated with 1 drop of single-masked vehicle per eye in each eye BID for a 14-day run-in period.	

Treatment Period. At Visit 2 Randomization (Day 1), subjects who continue to meet inclusion/exclusion criteria will be eligible for randomization to VVN001 Ophthalmic solution or vehicle.

Approximately 165 subjects will be randomized in this study at approximately 10 centers located in the United States. Subjects will be randomized to one of the following 3 treatment groups in a 1:1:1 ratio as follows:

Group A: 1% VVN001 administered BID (morning/evening)

Group B: 5% VVN001 administered BID (morning/evening)

Group C: Vehicle administered BID (morning/evening)

Following randomization, subjects will be instructed to self-administer 1 drop of IP per eye into each eye twice daily (morning/evening; Groups A, B, and C). Subjects will be instructed to return to the clinic to be evaluated at Study Visits 3, 4, 5 and 6 (Days 14, 28, 56 and 84 respectively). Subjects must take their morning eyedrop prior to Study Visits 3, 4 and 5. The last dose of IP and the final treatment visit (Visit 6) will occur upon completion of 84 (± 2) days of treatment. Subjects will be instructed not to use any topical eyedrops (e.g., over the counter artificial tears or topical ocular medications) other than the study medication during the study. Subjects will be released from the study at the end of Visit 6 (Day 84).

Safety Assessments (OU):

- Slit-Lamp Biomicroscopy and external eye exam
- Dilated Ophthalmoscopy
- Intraocular Pressure (IOP) measurement
- Best Corrected Visual Acuity (BCVA)
- Conjunctival Hyperemia Evaluation
- Drop Comfort/Tolerability Assessment

Efficacy Assessments (OU):

Signs

- Total Corneal Fluorescein Staining (tCFS score (0-20 point scale) at each clinic visit.
- Inferior region corneal staining score (0-4 point scale) at each clinic visit.
- CFS score by each individual subregion (0-4) at each clinic visit.
- Tear production (Schirmer test without anesthesia, mm/5 min) at each clinic visit.

Symptoms (subject reported)

- Eye dryness score (0-100 point Visual Analog Scale (VAS)) evaluated at each clinic visit.
- Eye discomfort score (0-100 point VAS) evaluated at each clinic visit.

- Symptom Assessment Questionnaire iN Dry Eye (SANDE) will be administered at each clinic visit.

Safety Endpoints:

- Ocular and non-ocular adverse events
- Slit-lamp biomicroscopy and external eye exam
- Conjunctival hyperemia score
- IOP
- Dilated Ophthalmoscopy
- BCVA
- Drop Comfort/Tolerability Assessment

Efficacy Endpoints:

Primary Endpoint:

Mean Change from baseline (Visit 2) to Day 84 (Visit 6) in inferior region of CFS (**iCFS**) using the modified National Eye Institute (NEI)/Industry Workshop (0-4 scale using 0.5 increments)

Secondary Endpoints:

The secondary endpoints will be evaluated in a hierarchical fashion and tested sequentially:

Key Secondary Endpoint:

1. Mean Change from baseline (Visit 2) to Day 84 (Visit 6) in the individual symptom of eye dryness (0 – 100 VAS scale).

Other Secondary Endpoints:

1. Mean Change from baseline (Visit 2) to Days 14 (Visit 3), 28 (Visit 4), 56 (Visit 5) and 84 (Visit 6) in total CFS (**tCFS**) using the modified NEI/Industry Workshop (0-20 scale; using 0.5 increments))
2. Mean Change from baseline (Visit 2) to Days 14 (Visit 3), 28 (Visit 4), Day 56 (Visit 5) and Day 84 (Visit 6) in each **individual subregion** (inferior (except for Day 84), superior, nasal, temporal, and central) of CFS using modified NEI/Industry Workshop (0-4 scale; using 0.5 increments))
3. Mean Change from baseline (Visit 2) to Days 14 (Visit 3), 28 (Visit 4) and 56 (Visit 5) in the individual symptom of eye dryness (0-100 VAS scale)
4. Mean Change from baseline (Visit 2) to Days 14 (Visit 3), 28 (Visit 4) 56 (Visit 5) and 84 (Visit 6) in the individual symptom of eye discomfort (0-100 VAS scale)
5. Mean Change from baseline (Visit 2) to Days 14 (Visit 3), 28 (Visit 4), 56 (Visit 5) and Day 84 (Visit 6) in SANDE.
6. Mean Change from baseline (Visit 2) to Days 14 (Visit 3), 28 (Visit 4), 56 (Visit 5) and Day 84 (Visit 6) in Schirmer.

Statistical Methods:

A detailed Statistical Analysis Plan (SAP) will be finalized prior to database lock.

General Considerations

All continuous study assessments will be summarized by treatment and visit (as applicable) using descriptive statistics (sample size (n), mean, median, standard deviation, minimum, and maximum). All categorical study assessments will be summarized by treatment and visit (as applicable) using frequency counts and percentages.

All study data will be listed by treatment, subject, and visit (as applicable).

Sample Size Rationale

A sample size of 55 subjects per treatment group will have 80% power to detect a treatment difference of 0.43 units with a common standard deviation 0.80 in iCFS score, and a treatment difference of 13.75 units with a common standard deviation 25.5 in eye dryness score at Visit 6/Day 84 using a t-test with a 0.05 two-sided significance level.

Eligibility Criteria:

At Visit 1 (Screening) and Visit 2 (Randomization) male or female subjects must meet the following criteria:

Inclusion Criteria:

1. Provide written informed consent prior to any study-related procedures and provide Health Insurance Portability and Accountability Act (HIPAA) authorization.
2. Are 18 years of age or older.
3. Are willing and able to follow instructions and willing to be present for the required study visits for the duration of the study.
4. Have a BCVA, using corrective lenses if necessary, in the qualifying eye(s) of +0.7 or better as assessed by Early Treatment of Diabetic Retinopathy Study (ETDRS) at the screening visit and randomization visit.
5. If a woman of child-bearing potential (WOCBP) not pregnant or lactating and not sexually active (i.e. abstinent) for 14 days prior to Visit 1 and willing to remain so through 30 days following Visit 6 or the last administration of the IP. Alternatively, a WOCBP who is not abstinent must have been using acceptable methods of birth control.
6. Are women who have undergone one of the following sterilization procedures at least 6 months prior to Visit 1:
 - a. Bilateral tubal ligation
 - b. Hysterectomy
 - c. Bilateral oophorectomy

7. Have a history of dry eye disease in both eyes supported by a previous clinical diagnosis or have a self-reported history of subjective complaints for at least 6 months prior to screening
8. Are currently using artificial tears and have been using within 30 days of the screening visit.
9. Have an Eye dryness score ≥ 40 at Visit 1 and ≥ 35 at Visit 2, one score for both eyes (0-100 point VAS)
10. Have ongoing dry eye disease in the same eye or both eyes, as defined by all of the following criteria in the study eye and the same eye at Visit 1 and Visit 2:
 - a. Inferior CFS (iCFS) score of ≥ 2 (NEI; 0-4 scale; using 0.5 unit increments)
 - b. Have a Schirmer score (without anesthesia) of ≥ 1 and ≤ 7 mm/5 min.
11. Have in the opinion of the Investigator, normal lid anatomy.
12. Are willing to withhold artificial tears for the duration of the study.

Exclusion Criteria:

1. Have a known hypersensitivity or contraindication to the IP or components of IP.
2. Have a Schirmer score (without anesthesia) of <1 or >7 mm/5 min in the study eye.
3. Within 14 days prior to screening (Visit 1) have taken:
 - a. Topical ocular antibiotics or systemic antibiotics taken for an ocular condition
 - b. Serum tears
 - c. Topical ocular non-steroidal anti-inflammatory drugs (NSAIDs)
 - d. Topical ocular or oral antihistamines or mast cell stabilizers
 - e. Topical ocular or nasal vasoconstrictors (Phenylephrine as part of an ocular evaluation is allowed)
4. Within 30 days prior to screening (Visit 1) have taken/used:
 - a. Ocular, inhaled or intranasal or dermatologic corticosteroids
 - b. Topical cyclosporine (Restasis[®] and Cequa[®])
 - c. Topical ophthalmic lifitegrast (Xiidra[®])
 - d. Intranasal Tear Neurostimulation
 - e. Any topical ophthalmic medications or makeup for eyelash growth
5. Have any prior use of isotretinoin (Accutane[®]).
6. Within 60 days prior to screening (Visit 1), or during the study, have altered the dosage or anticipate alterations to the dose of the following:
 - a. Anticholinergics (if used on a chronic basis)
 - b. Antidepressants (if used on a chronic basis)
 - c. Systemic immunosuppressive agents

- d. Oral contraceptives
- e. Oral or injectable corticosteroids (e.g., prednisone. Prednisone dose must be less than 11 mg/day)

7. Expect to use any Cannabidiol products during the study.

8. Have history of uncontrolled glaucoma, IOP over 21 mmHg in either eye at the screening visit or are being treated with eye drops for glaucoma in the study eye. Or the subject has had laser or surgery for glaucoma in the study eye within 90 days of the study.

9. Subjects who cannot suspend the use of contact lenses from Visit 1 and throughout the study.

10. Subjects who have a history of Anterior Basement Membrane Corneal Dystrophy.

11. Subjects who have had a corneal transplant or similar corneal surgery (DALK, DSEK, DMEK, etc.).

12. History of incisional ocular surface surgery, including but not limited to refractive, LASIK, Pterygium surgery within 6 months prior to Visit 1.

13. Any incisional intraocular surgical procedure within 12 months prior to Visit 1; or any planned ocular surgical procedure during the study period.

14. History of yttrium aluminum garnet-laser posterior capsulotomy or any laser ocular surgery in past 90 days prior to Visit 1.

15. Non-compliance (<80%) with Vehicle Run-In administration.

16. Have had eyelid surgery within the past 6 months.

17. Have a congenitally absent lacrimal gland or meibomian glands.

18. Have had cauterization of the punctum or have had non-dissolvable (silicone) or short term dissolvable punctal plugs inserted or removed within the 30 days prior to the screening or planned during the study. Have had long-term dissolvable plugs within 3 months of Visit 1.

19. Subjects who have active or have had an outbreak of herpetic keratitis within one year of Visit 1 or subjects who are on chronic oral antivirals for herpetic disease.

20. Have a diagnosis of:

- a. Ongoing ocular infection, lid margin disorders such as blepharitis (including staphylococcal, demodex or seborrheic) are allowed if not requiring treatment with ocular or systemic antibiotics at Visit 1 or intended treatment during the study.
- b. Meibomian gland disease requiring mechanical meibomian gland expression within the past 3 months.
- c. Excessive lid laxity, floppy eyelid syndrome, ectropion, entropion in either eye or moderate to severe pinguecula or pterygia in the study eye, per the opinion of the Investigator.
- d. Stevens-Johnson syndrome

- e. Significant conjunctival scarring in the judgment of the Investigator
- f. Severe/serious ocular condition that in the judgment of the Investigator opinion could confound study assessments or limit compliance.
- g. Severe/serious systemic disease or uncontrolled medical condition that in the judgment of the Investigator could confound study assessments or limit compliance.

21. Have a documented history of ocular allergies, which, in the judgment of the Investigator, are likely to have an acute increase in severity due to the expected timing of the exposure to the allergen to which the subject is sensitive. Subjects sensitive to seasonal allergens that are not expected to be present during the study are permitted.

22. Be current cigarette smokers.

23. Have been exposed to an investigational drug within the preceding 30 days or previously randomized in this study.

24. Be an employee of the site that is directly involved in the management, administration, or support of this study or be an immediate family member of the same.

25. Have a known history of alcohol and/or drug abuse within the past 5 years.

[figure not shown]
26. In the opinion of the Investigator or study coordinator, be unwilling or unable to comply with the study protocol or unable to successfully instill eye drops.

Randomization Criteria:

At Visit 2, the subject must continue to meet criteria outlined at Visit 1 except: Eye dryness score ≥ 35 one score for both eyes (0-100 point VAS) will qualify.

Study Schematic:

Figure 1 Study Schematic

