3. STUDY DESIGN

3.1. OVERALL DESIGN OF THE STUDY

This is a Phase 2a, multi-center, double-masked, randomized, vehicle-controlled, parallel-group study designed to evaluate the safety and tolerability and to explore the efficacy activity of VVN001 Ophthalmic solution versus vehicle in subjects with dry eye disease. The study will consist of two periods over 14-weeks total as follows:

1. Screening/ run-in period (Day -14 to Day -1)
2. Treatment period (Day 1 to Day 84)

Screening/Run-In Period:

At Visit 1 Screening (Day 1 minus 14 days), subjects who meet screening inclusion/exclusion criteria will begin a two-week run-in period during which they will be treated with 1 drop of single-masked vehicle per eye in each eye BID for a 14-day run-in period.

Treatment Period:

[figure not shown]
At Visit 2 Randomization (Day 1), subjects who continue to meet inclusion/exclusion criteria will be eligible for randomization to VVN001 Ophthalmic solution or vehicle.

Approximately 165 subjects will be randomized in this study at approximately 10 centers located in the United States (US). Subjects will be randomized to one of the following 3 treatment groups in a 1:1:1 ratio as follows:

- Group A: 1% VVN001 administered BID (morning/evening)
- Group B: 5% VVN001 administered BID (morning/evening)
- Group C: Vehicle administered BID (morning/evening)

Following randomization, subjects will be instructed to self-administer 1 drop of IP per eye into each eye twice daily (morning/evening; Groups A, B, and C). Subjects will be instructed to return to the clinic to be evaluated at Study Visits 3, 4, 5 and 6 (Days 14, 28, 56 and 84 respectively). Subjects must take their morning eyedrop prior to Study Visits 3, 4 and 5. The last dose of IP and the final treatment visit (Visit 6) will occur upon completion of 84 days of treatment. Subjects will be instructed not to use any topical eyedrops (e.g., over the counter artificial tears or topical ocular medications) other than the study medication during the study. Subjects will be released from the study at the end of Visit 6 (Day 84). See [Figure 2](#) for a Schematic of the study visits.

Figure 2

Safety Assessments

Safety assessments in the study will be evaluated in both eyes (OU) and will include:

- Biomicroscopy and external eye exam
- Dilated ophthalmoscopy
- Intraocular pressure (IOP) measurement
- Best Corrected Visual Acuity (BCVA)
- Conjunctival Hyperemia Evaluation
- Drop Comfort/Tolerability Assessment

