4.2. EXCLUSION CRITERIA

At Visit 1, for subjects to be eligible for study participation they may not:

1. Have a known hypersensitivity or contraindication to the IP or IP components.
2. Have a Schirmer score (without anesthesia) of <1 or >7mm/5 min in the study eye.
3. Within 14 days prior to screening (Visit 1) have taken:
 - a. Topical ocular antibiotics or systemic antibiotics taken for an ocular condition.
 - b. Serum tears
 - c. Topical ocular non-steroidal anti-inflammatory drugs (NSAIDs)
 - d. Topical ocular or oral antihistamines or mast cell stabilizers
 - e. Topical ocular or nasal vasoconstrictors (Phenylephrine as part of an ocular evaluation is allowed)
4. Within 30 days prior to screening (Visit 1) have taken/used:
 - a. Ocular, inhaled, dermatologic or intranasal corticosteroids
 - b. Topical cyclosporine (Restasis® and Cequa®)
 - c. Topical ophthalmic lifitegrast (Xiidra®)
 - d. Intranasal Tear Neurostimulation
 - e. Any topical ophthalmic medications or makeup for eyelash growth.
5. Have any prior use of isotretinoin (Accutane®).
6. Within 60 days prior to screening (Visit 1), or during the study, have altered the dosage or anticipate alterations to the dose of the following:
 - a. Anticholinergics (if used on a chronic basis)
 - b. Antidepressants (if used on a chronic basis)
 - c. Systemic immunosuppressive agents
 - d. Oral contraceptives
 - e. Oral or injectable corticosteroids (e.g., prednisone. Prednisone dose must be less than 11 mg/day)
7. Expect to use any Cannabidiol products during the study.
8. Have history of uncontrolled glaucoma in either eye, IOP over 21 mmHg at the screening visit or are being treated with eye drops for glaucoma in either eye. Or the subject has had laser or surgery for glaucoma in the study eye within 90 days of the study.
9. Subjects who cannot suspend the use of contact lenses from Visit 1 and throughout the study.

10. Subjects who have a history of Anterior Basement Membrane Corneal Dystrophy.
11. Subjects who have had a corneal transplant or similar corneal surgery (DALK, DSEK, DMEK, etc.).
12. History of incisional ocular surface surgery, including but not limited to refractive, LASIK, Pterygium surgery within 6 months prior to Visit 1.
13. Any incisional intraocular surgical procedure within 12 months prior to Visit 1; or any planned ocular surgical procedure during the study period.

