4.4. STUDY EYE

Subjects must replicate the following findings in the same eye at Visits 1 and 2 in order to be considered for further study eligibility: 1) Inferior CFS score ≥ 2 (0 – 4 scale) and (2) Schirmer score STT without anesthesia ≥ 1 and ≤ 7 mm, at Visits 1 and 2. If both eyes meet the two criteria above, the eye with the greater inferior CFS at Visit 2 will be selected as the study eye. If both eyes have an equal inferior CFS score at Visit 2, the eye with the lowest STT value at Visit 2 will be designated as the study eye. If both eyes have equal score in inferior CFS scores at Visit 2, the right eye (OD) will be selected as the study eye.

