Contact Lenses or current use of eye drops for glaucoma.	At Screening and throughout study

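### Exclusion 8 has two conflicting versions: the synopsis bars glaucoma drops in the study eye only, Section 4.2 bars them in either eye, and the synopsis version also conflicts with the eyedrop ban and Table 1

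*Protocol*

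**What the plan says.** **Synopsis, exclusion 8.** The criterion opens with "Have history of uncontrolled glaucoma, IOP over 21 mmHg in either eye at the screening visit" and goes on to cover subjects who "are being treated with eye drops for glaucoma in the study eye".

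**Section 4.2, exclusion 8.** The same criterion opens with "Have history of uncontrolled glaucoma in either eye, IOP over 21 mmHg at the screening visit" and covers subjects who "are being treated with eye drops for glaucoma in either eye".

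**Other eyedrops.** Section 3.1 states: "Subjects will be instructed not to use any topical eyedrops (e.g., over the counter artificial tears or topical ocular medications) other than the study medication". The synopsis carries the same instruction under Study Design ("Subjects will be instructed not to use any topical eyedrops"). Neither place makes an exception for the fellow eye or for glaucoma treatment.

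**Table 1 (Section 4.12).** The list of what is not permitted includes "Contact Lenses or current use of eye drops for glaucoma". Its time column runs from screening through the whole study, and no eye is named.

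**Study eye (Section 4.4).** "If both eyes meet the two criteria above, the eye with the greater inferior CFS at Visit 2 will be selected as the study eye".

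**Visit 1 (Section 6.1.1).** Eligibility is determined, the run-in kit is dispensed, and the visit closes with an instruction to stop all prohibited medications.

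**The concern.** An exclusion criterion should give the same answer on whichever page the site reads it. Here it does not, and the subject on whom the two versions disagree is one under treatment for glaucoma. If a site works from the synopsis, that subject can enter run-in and then meet two other rules that forbid the drops. The protocol does not say what should happen next. The stake is mainly patient safety and consistent eligibility across about 10 centers. There is a lesser stake in the supportive non-study-eye analyses, because the eye in question would be the non-study eye.

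**Working it through.** No arithmetic applies. The check sets the passages side by side.

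**1. Is one version superseded?** No. The protocol is the original issue of 17 June 2020, and SAP Section 1.1 names the protocol of that date as its basis. Both versions are current.

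**2. Which eye does each clause of exclusion 8 name?**

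| Clause | Synopsis | Section 4.2 |
|---|---|---|
| Uncontrolled glaucoma | none named | either eye |
| IOP over 21 mmHg at screening | either eye | none named |
| Current glaucoma drops | study eye | either eye |
| Glaucoma laser or surgery within 90 days | study eye | study eye |

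Three of the four clauses differ. For the first two, a reader may take silence to mean any eye, so the practical difference may be slight. For the drops clause the two texts cannot both be followed.

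**3. Who is treated differently?**

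| Glaucoma drops used in | Synopsis excl. 8 | Section 4.2 excl. 8 | Eyedrop ban and Table 1 |
|---|---|---|---|
| Study eye | excluded | excluded | not permitted |
| Both eyes | excluded | excluded | not permitted |
| Non-study eye only | passes | excluded | not permitted |

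Only the last row is in dispute. In that row the synopsis criterion conflicts with Section 4.2, with Table 1, and with the eyedrop ban in the synopsis itself.

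**4. What follows if a site applies the synopsis wording?** At the end of Visit 1 the subject is told to stop prohibited medications, and Table 1 makes glaucoma drops one of them. The subject then either stops the drops or continues them as a protocol deviation. No third course is written.

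**5. Can the synopsis clause be decided at Visit 1?** The qualifying findings must be repeated in the same eye at both visits. If only one eye qualifies at Visit 1, the study eye can only be that one and the clause can be applied. If both qualify, the choice rests on Visit 2 staining and then Visit 2 Schirmer values. For a subject with drops in one of two qualifying eyes, the clause is therefore open at Visit 1. The recheck at Visit 2 (Sections 4.3 and 6.1.2) can settle it, but only after the stop instruction and the two-week run-in.

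**6. How many subjects?** The documents give no count or prevalence, so no figure can be derived.

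**The case against.** The strongest reply is that other text already keeps this subject out. Section 4.3 ties randomization to Sections 4.1 and 4.2, not to the synopsis, and Section 4.2 has the either-eye wording. Table 1 bars glaucoma drops from screening onward. Exclusion 26 lets a site turn away anyone unable to comply. In the Visit 1 order, eligibility is decided before anyone is told to stop a medication. The study-eye timing problem is also not special to this clause: exclusion 2, exclusion 20c and the laser or surgery clause of exclusion 8 all refer to the study eye, and the criteria are rechecked at Visit 2.

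Most of this stands, and it limits the problem to sites that work from the synopsis wording. It does not remove the contradiction. The synopsis has its own randomization criteria, which refer back to the Visit 1 criteria and not to Section 4.2, and exclusion 26 is discretionary.

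A reader might infer more than the documents support:

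- *That such a subject cannot be managed at all.* The text leaves two courses, stopping or deviating. The defect is that the protocol does not reconcile them.
- *That stopping the drops would produce a false IOP signal in the non-study-eye safety tables.* No passage gives the effect of stopping. IOP is measured again at Visit 2, after the run-in. The SAP names Day 1 as the efficacy baseline (Section 4.7) and defines no separate one for IOP. If Visit 2 serves for IOP too, a rise during run-in is already in the baseline. Allocation is randomized 1:1:1, so no systematic difference between arms follows.
- *That the main efficacy results are at risk.* The primary endpoint is inferior staining in the study eye, the key secondary is one dryness score per subject, and protocol Section 9.1.3 calls the non-study-eye analyses supportive. No effect on either main endpoint is shown.

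**Conclusion.** The point holds as an internal inconsistency in the current protocol. Exclusion 8 gives opposite answers for a subject on glaucoma drops in the non-study eye only, and the synopsis answer also conflicts with the eyedrop ban and Table 1. Its reach depends on two things the documents do not report: how many screened subjects use glaucoma drops in one eye only, and whether any site applied the synopsis wording. The number may be small. It is worth correcting because it concerns ongoing glaucoma treatment and because eligibility should not depend on the page consulted. It is not a ground for doubting the primary or key secondary analysis.

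**What to change.** Reconcile five places: synopsis exclusion 8, the synopsis eyedrop instruction, Section 3.1, Section 4.2 exclusion 8, and Table 1. Exclusion 8 should then have one wording in both locations, state the eye for each clause (uncontrolled glaucoma, IOP over 21 mmHg, glaucoma drops, laser or surgery), and agree with the eyedrop ban and Table 1. If any clause depends on the study eye, say at which visit it is judged. Which rule to adopt is for the sponsor's clinical team; this review does not choose one.

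The cost is protocol wording, with the IRB approval that Section 10.5.1 requires for amendments. No procedure, visit or analysis changes because of the reconciliation itself. If subjects have already been randomized, the size of the problem can be read from data the plan already collects: SAP Section 4.8.5 summarizes ocular prior and concomitant medications separately for study and non-study eyes.
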